5.6.2 Management of Overdose

Weight-based dosing for tisotumab vedotin is based on the patient's actual body weight, with the exception of patients weighing greater than 100 kg. Dosing will be based on 100kg for these individuals. **The maximum dose permitted per infusion in this study is 90 mg or 120 mg for patients receiving the dose-dense regimen and 200 mg for patients receiving the Q3W regimen. If the dose for the dose-dense regimen is de-escalated to 0.65 mg/kg, the maximum dose permitted per infusion will be 65 mg.**

In the event of an overdose of tisotumab vedotin $\geq 10\%$, study personnel should:

- Care for and medically stabilize the patient until there is no immediate risk of complications or death, if applicable. There is currently no known antidote for an overdose of tisotumab vedotin.
- Consider growth factor support and monitoring of coagulation parameters with appropriate intervention as needed.
- Notify the sponsor's medical monitor as soon as they become aware of the overdose, to discuss details of the overdose (e.g., exact amount of tisotumab vedotin administered, patient weight) and adverse events, if any.

5.7 Treatment Compliance

Study drug administration will be performed by study site staff and documented in source documents and the CRF. In addition, patients will be provided with a patient diary and instructed to record details of prophylactic eye drop usage each day.

6 STUDY ACTIVITIES

6.1 Schedule of Events

Adverse events and concomitant medications will be recorded from Day 1 (predose) through the safety reporting period (see Section 7.7.8). Any study protocol-related adverse event (defined in Section 7.7.8.1) as well as any concomitant medications given for treatment of the adverse event, should be recorded from the time of informed consent. A schedule of events is provided in Appendix A. Study activities are listed by visit in this section and descriptions of all study assessments are presented in Section 7.

For all treatment cycles, clinical laboratory assessments (serum chemistry panel, complete blood count [CBC] with differential, coagulation parameters, and Hemoglobin A1c [HgbA1c]) as well as physical exam, weight, and ECOG performance status may be performed within 1 day prior to administration of study drug. The results from all relevant clinical laboratory assessments must be reviewed prior to dosing.

Tumor biopsies performed outside protocol-specified time points during the study should be made available to the sponsor if feasible and if the patient has consented to submission of these samples (see Section 7.5.2). Biopsies performed at protocol-specified time points must be submitted to the sponsor.

Procedures listed below include only those that occur in the clinic or on the same day that a patient visits the clinic. See [Appendix C](#) for the preventative eye therapy schedule and dosing diary schedule. The PRO-CTCAE patient-reported outcomes questionnaire should be collected at baseline and weekly (± 2 days) starting on Cycle 1 Day 1 through the end of treatment ([Appendix A](#)).

6.2 Screening Visit (Days [-28] to 1)

- Informed consent
- Study eligibility per inclusion/exclusion criteria
- Blood collection for CA-125 (results to be submitted to central laboratory)
- Medical history (see Section 7.1)
- Height and weight
- Physical exam
- Vital signs
- Eye exam performed by investigator (see Section 7.7.5 and [Appendix C](#))
- Ophthalmologic evaluation performed by ophthalmologist (see Section 7.7.4)
- Electrocardiogram (ECG)
- Biopsy collection (See Section 7.1.1)
- Imaging

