6.2.1 Baseline Visit (Days -7 to Day 1)

- Pregnancy test for patients of childbearing potential
- CBC with differential (results to be submitted to central laboratory)
- Chemistry panel (results to be submitted to central laboratory)
- Calculation of eGFR (See Section 7.7.2)
- Coagulation parameters (fibrinogen, INR, PT, and aPTT) (results to be submitted to central laboratory)
- HgbA1c (results to be submitted to central laboratory)
- ECOG performance status
- Parts A and B, US patients only: patient-reported outcomes questionnaires (all questions)

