9.2.3 CA-125 Response Rate

CA-125 response rate is defined as the proportion of patients who have at least a 50% reduction in CA-125 value from baseline. The response must be confirmed in a subsequent sample collected ≥ 28 days after the prior sample. The absolute value of the confirmatory sample must be $\leq 110\%$ of the prior sample. Only patients who have an elevated baseline CA-125 value of $\geq 2 \times$ ULN and within 2 weeks prior to the first dose of study drug will be included in the analysis.

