9.3.1.7 Analysis Sets

The full analysis set (FAS) includes all patients who received any amount of study drug. All efficacy analyses will be based on the FAS.

The safety analysis set includes all patients who received any amount of study drug, and thus is equivalent to the FAS. All safety analyses will be based on the safety analysis set.

The DLT evaluable analysis set includes all patients who received any amount of study drug and have completed the DLT evaluation period or have experienced a DLT. The DLT evaluable set applies only to the safety run-in cohort.

The efficacy-evaluable (EE) analysis set includes patients who received any amount of study drug and had at least one post-baseline disease assessment per RECIST v1.1 or discontinued from the study or started subsequent cancer therapy. The EE analysis set will be used for supplemental analysis of efficacy endpoints as applicable.

The CA-125 evaluable analysis set includes patients with ovarian cancer who have an elevated baseline CA-125 value of $\geq 2 \times$ ULN and within 2 weeks prior to the first dose of study drug. The CA-125 evaluable analysis set will be used for the analysis of CA-125 response rate.

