APPENDIX A: SCHEDULE OF EVENTS

SCHEDULE OF EVENTS: Q3W REGIMEN

		Screening/Baseline	Every 21-day cycle	Cycle 1 only		EOT	F/U
Day		D -28 to 1	D -7 to 1	D1 ^A	D2	D3	Within 30-37D of last dose ^B
Visit window				±1d		±1d	Every 12 wks ^C ±7d
Informed consent	X						
Inclusion/Exclusion criteria	X						
Physical exam	X			X ^F			
Medical history	X						
Height and weight	X			X ^D			
Vital signs	X			X			X
CBC with differential ^E				X ^F		X	X
Chemistry panel ^E				X ^F		X	X
eGFR				X			
Coagulation parameters ^E				X ^F		X	X
Pregnancy test (patients of childbearing potential) ^G				X ^F		X	X ^H
HgbA1c ^F	X						X
Ocular Safety Measures				See schedules in Appendix C			
ECOG performance status		X		X ^F			X
ECG	X						X
Concomitant medications				Related to study procedures ^I			
Adverse event collection				X			
Study drug administration							
Biopsy collection	X						
Blood/tissue sample collection				See schedules in Appendix B and Appendix C			
Imaging	X			Every 6 weeks ^J		X ^K	X ^{J,N}
CA-125 blood collection	X			Every 6 weeks ^L		X ^K	
Parts A and B US only: Patient-Reported Outcomes: PROMIS ^M	Questionnaires					X	
Parts A and B US only: Patient-Reported Outcomes: PRO-CTCAE ^M	Questionnaires	X		X ^F			
Subsequent Anti-Cancer Therapy Status				To be collected weekly ±2 days, starting on C1D1 and continuing weekly through EOT ^F		X	X
Survival Status						X	X

A Day 1 of cycle 1 is to be performed no more than 28 days after the screening visit. Day 1 of cycle 2 is to be performed 21 days \pm 3 days after Day 1 of cycle 1. Day 1 of cycle 3 is to be performed 21 days \pm 1 days after Day 1 of cycle 2, etc.

B EOT evaluations should be obtained before the initiation of non-protocol therapy. If EOT evaluations are completed before 30 days following the last study treatment, conduct a phone screen 30–37 days following the patient's last study treatment to ensure that no changes in AE profile have occurred.

C A telephone call should be performed in order to collect information of survival and new anti-cancer treatment as specified in Section [6.7](#).

D Height measurement needed at screening visit only.

E Clinical laboratory testing is to be performed locally. With the exception of pregnancy testing, results are to be submitted to the central laboratory.

F If this assessment occurs within 1 day prior to Cycle 1, Day 1, it does not need to be repeated at Visit 1.

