### **5.6 CA-125 Evaluable Analysis Set**

The CA-125 evaluable analysis set includes patients who have an elevated baseline CA-125 value of  $\geq 2 \times$  ULN (upper limit of normal) within 2 weeks prior to the first dose of study drug. The CA-125 evaluable analysis set will be used for the analysis of CA-125 response rate.

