#### 7.5.2.2 CA-125 Response Rate

Baseline CA-125 is the most recent non-missing measurement no more than 14 days prior to the first dose of study drug.

CA-125 response rate is defined as the proportion of patients who have at least a 50% reduction in CA-125 value from baseline. The response must be confirmed in a subsequent sample collected  $\geq 28$  days after the prior sample. The value of the confirmatory sample must

be  $\leq 110\%$  of the prior sample. The CA-125 evaluable analysis set will be used for the analysis of CA-125 response rate.

In addition, summary statistics of CA-125 values and changes from baseline will be tabulated by scheduled visit using the FAS.

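### The only scheduled pre-dose CA-125 draw may be taken up to 28 days before dosing, but the analysis accepts a baseline no older than 14 days, so a compliant draw can make a patient non-evaluable

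*Protocol*

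**What the plan says.** **Collection.** Protocol 6.2 (screening visit, Days -28 to 1) lists "Blood collection for CA-125 (results to be submitted to central laboratory" with no narrower window of its own. Footnote A to both Appendix A schedules allows a long gap before dosing: "Day 1 of cycle 1 is to be performed no more than 28 days after the screening visit". Section 6.2.1, headed "Baseline Visit (Days -7 to Day 1", repeats CBC, chemistry, coagulation and HgbA1c but does not list CA-125. The Day 1 lists for the two regimens (6.3.1 and 6.4.1) do not list it either. After the screening draw, Appendix A shows CA-125 every 6 weeks with imaging and at end of treatment.

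**Analysis.** Four places set a two-week limit:
- Protocol 9.2.3: only patients with an elevated baseline value "within 2 weeks prior to the first dose of study drug will be included in the analysis".
- Protocol 9.3.1.7, defining the evaluable set: "within 2 weeks prior to the first dose of study drug. The CA-125 evaluable analysis set will be used".
- SAP 5.6, defining the same set: "within 2 weeks prior to the first dose of study drug".
- SAP 7.5.2.2: "Baseline CA-125 is the most recent non-missing measurement no more than 14 days prior to the first dose of study drug".

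SAP 7.5.2.2 also plans a second use of that baseline: "summary statistics of CA-125 values and changes from baseline will be tabulated by scheduled visit using the FAS".

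**The concern.** The schedule and the analysis use different windows for the same sample, and nothing requires a repeat when the first sample becomes too old, for example because dosing slips. The mismatch lies inside the protocol (6.2 and Appendix A against 9.2.3 and 9.3.1.7) as well as between the protocol and the SAP.

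Three outputs are exposed:
- **CA-125 response rate.** A patient at or above 2 x ULN whose only sample is more than 14 days old leaves the denominator.
- **Combined RECIST/CA-125 response.** Under SAP 7.5.2.3, patients outside the evaluable set are assessed on CA-125 for progression only. The table rows that turn RECIST SD, NE or late PD into PR all need a CA-125 response, so they are closed to these patients.
- **Change from baseline in the FAS.** A patient at any CA-125 level with only an older sample has no baseline under SAP 7.5.2.2.

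In each case data would be lost through screening logistics rather than through anything about the patient's disease or response.

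**Working it through.** The documents give no expected size for the CA-125 evaluable set and no precision figure for CA-125, so there is no stated number to reproduce. The check is a comparison of the two windows by day.

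**Inputs**
- Permitted collection window: Day -28 to Day 1 (Protocol 6.2; the 28-day maximum gap is in Appendix A footnote A).
- Accepted baseline: at most 14 days before first dose (SAP 7.5.2.2; same limit in SAP 5.6 and Protocol 9.2.3 and 9.3.1.7).
- Day numbering: first dose is Day 1 and the day before it is Day -1, so there is no Day 0 (SAP 6.4.1). A sample on Day -k is therefore k days before first dose.

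**Count**
- Permitted days: Days -28 to -1 (28) plus Day 1 pre-dose (1) = 29.
- Accepted by the analysis: Days -14 to -1 (14) plus Day 1 pre-dose (1) = 15.
- Permitted but not accepted: Days -28 to -15 = 29 - 15 = 14.
- Share of permitted days not accepted: 14/29 = 48%. Leaving Day 1 out, it is 14/28 = 50%.

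**Effect on the combined endpoint (table in SAP 7.5.2.3)**

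| RECIST | With CA-125 response | No CA-125 response, no CA-125 PD |
|---|---|---|
| CR | CR if normalized, otherwise PR | PR |
| PR | PR | PR |
| SD | PR | SD |
| NE | PR | no row given |
| PD more than 28 days from CA-125 response | PR | PD |

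A patient who cannot be scored as a CA-125 responder still counts as a responder if RECIST gives CR or PR. The loss falls on the SD, NE and late-PD rows.

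**After the fix.** If a value within 14 days before first dose is required, the number of compliant draw dates that fail the analysis limit falls from 14 to 0.

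**The case against.** The best defence is that a usable, compliant draw is always available. Any draw from Day -14 to pre-dose Day 1 meets both rules, and sites hold a protocol that prints the two-week limit. This is right as far as it goes: the result is a gap in the schedule, not a certain loss. But the limit appears only in the statistical sections, and the visit lists that sites work from do not repeat it.

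Other safeguards are partial:
- Section 7.1 names CA-125 among items needed at either screening or baseline, but it refers back to 6.2 and Appendix A, which place the draw at screening.
- The general baseline rule in SAP 6.4.1 (latest pre-dose value) applies only where nothing else is specified, and SAP 7.5.2.2 specifies something else.
- Clinical laboratory tests are run locally (7.7.2), so an unscheduled value could rescue a patient, but none is required.
- The size of each analysis set will be reported (Protocol 9.3.2, SAP 7.1), but not the reason for exclusion. Loss through sample age would look the same as CA-125 below 2 x ULN.

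It also stands that the efficacy analyses are descriptive (SAP 7.5). For the CA-125 response rate itself, losing patients because of a pre-treatment draw date mainly costs precision; nothing in the documents points to bias in that rate.

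Two stronger readings are tempting and do not hold. A reader might infer that pairing CA-125 with imaging (within 5 days) ties the baseline draw to an early screening scan and so forces it outside the limit. In both Appendix A schedules that footnote (L) is attached to the on-treatment every-6-weeks entry, not to the screening mark. In 6.5 the pairing sentence follows a scan schedule counted from first dose, and its wording there and in 7.2 asks for closeness only as far as possible.

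A reader might also infer that affected patients cannot be classified for CA-125 progression, so that a RECIST response which CA-125 PD should override would stand. Footnote b of the combined-response table refers to CA-125 status before treatment, not to the 14-day baseline, and SAP 7.5.2.3 expressly assesses these patients for progression. Which pre-dose value sets that status is a separate wording query.

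**Conclusion.** The conflict is real. Following the schedule exactly can remove an otherwise eligible patient from the CA-125 evaluable set, close the CA-125 route to PR in the combined response, and leave no baseline for the FAS table. The measurable size is 14 of 29 permitted draw days, counted with the SAP's no-Day-0 convention and with no unscheduled repeat.

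The 48% should not be read as the proportion of patients lost. The documents do not say when sites draw, and the number affected could be zero. For the same reason no effect on the width of a confidence interval or on the combined rate can be calculated from the documents.

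The reach is limited to descriptive secondary outputs. Confirmed ORR by RECIST and the Part B predictive-probability rule do not use CA-125. The correction is worth making because it is cheap and removes the gap, not because the trial's main conclusion is at risk.

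**What to change.** Amend Protocol 6.2, 6.2.1 and both Appendix A schedules so that a CA-125 value within 14 days before first dose must be available. If the screening sample is older than that, repeat it pre-dose with the bloods already taken at the baseline visit (Days -7 to 1). The analysis definitions in Protocol 9.2.3 and 9.3.1.7 and SAP 5.6 and 7.5.2.2 can stay as they are.

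The cost is schedule wording in the next amendment and one extra tube for some patients at an existing blood visit.

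Optionally, for patients already dosed, report in the SAP outputs how many are outside the CA-125 evaluable set only because of sample age. This needs no new data and would show whether the gap had any effect.

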6.2.1 Baseline Visit (Days -7 to Day 1)

- Pregnancy test for patients of childbearing potential
- CBC with differential (results to be submitted to central laboratory)
- Chemistry panel (results to be submitted to central laboratory)
- Calculation of eGFR (See Section 7.7.2)
- Coagulation parameters (fibrinogen, INR, PT, and aPTT) (results to be submitted to central laboratory)
- HgbA1c (results to be submitted to central laboratory)
- ECOG performance status
- Parts A and B, US patients only: patient-reported outcomes questionnaires (all questions)

6.3 Treatment Period (Q3W Regimen only)

6.3.1 Day 1 (± 1 day), All treatment cycles (exceptions noted)

- Cycle 1 only: Prior to dosing, confirm patient eligibility per inclusion/exclusion criteria
- Weight
- Physical Exam
- Predose vital signs
- ECOG Performance status (If Baseline Visit activities occur within 1 day prior, this assessment does not need to be repeated at Cycle 1, Day 1)
- Chemistry panel (results to be submitted to central laboratory; if Baseline Visit activities occur within 1 day prior, this assessment does not need to be repeated at Cycle 1, Day 1)
- CBC with differential (results to be submitted to central laboratory; if Baseline Visit activities occur within 1 day prior, this assessment does not need to be repeated at Cycle 1, Day 1)
- Pregnancy test for patients of childbearing potential (If Baseline Visit activities occur within 1 day prior, this assessment does not need to be repeated at Cycle 1, Day 1)
- Coagulation parameters (fibrinogen, INR, PT, and aPTT) (results to be submitted to central laboratory; if Baseline Visit activities occur within 1 day prior, this assessment does not need to be repeated at Cycle 1, Day 1)
- Eye exam performed by investigator
- Predose blood sample for PK evaluation (within 24 hours) (Cycles 1, 2, 3, 4, 5, and every other cycle thereafter)
- Predose blood sample for antitherapeutic antibody (ATA) evaluation (within 24 hours) (Cycles 1, 2, 3, 4, 5, and every other cycle thereafter)
- Predose blood sample for plasma proteomic analysis (within 24 hours) (Cycles 1, 2, 3, 4, 5, and every other cycle thereafter)
- Predose blood sample for plasma mutational analysis (within 24 hours) (Cycles 1, 2, 3, 4, 5, and every other cycle thereafter)
- Predose blood sample for plasma exosome analysis (within 24 hours) (Cycles 1, 2, 3, 4, 5, and every other cycle thereafter)
- Predose blood sample for PBMC immune subsets analysis (within 24 hours) (Cycles 1, 2, 3, and 4 only)
- Ocular premedication and preventative eye therapy (see Section 5.4 and [Appendix C](#))
- Ensure patient completes dosing diary
- Parts A and B, US patients only: Patient-reported outcomes questionnaires (all questions). If Baseline Visit activities occur within 1 day prior, this assessment does not need to be repeated at Cycle 1, Day 1.
- Tisotumab vedotin administration

- Blood samples for PK evaluation (all time points from end of infusion)
 - End of infusion (+ 15 minutes) (Cycles 1, 2, 3, 4, 5, and every other cycle thereafter)
 - 1 hour (\pm 15 minutes) (Cycles 1 and 2 only)
 - 5 hours (\pm 30 minutes) (Cycles 1 and 2 only)
- Blood samples for plasma proteomic analysis (all time points from end of infusion)
 - End of infusion (+15 minutes) (Cycles 1, 2, 3, 4, 5, and every other cycle thereafter)
 - 1 hour (\pm 15 minutes) (Cycles 1 and 2 only)
 - 5 hours (\pm 2 hours) (Cycles 1 and 2 only)

6.3.2 Cycle 1 and 2, Day 2

- Preventative eye therapy (see Section [5.4](#) and [Appendix C](#))
- Ensure patient completes dosing diary

6.3.3 Cycle 1 and 2, Day 3

- Preventative eye therapy (see Section [5.4](#) and [Appendix C](#))
- Blood sample for PK evaluation (48 hours \pm 4 hours after the end of infusion)
- Blood sample for plasma proteomic analysis (48 hours \pm 4 hours after the end of infusion)
- Ensure patient completes dosing diary

6.3.4 Cycle 1 Day 8 (\pm 1 day)

- CBC with differential (results to be submitted to central laboratory)
- Chemistry panel (results to be submitted to central laboratory)
- Coagulation parameters (fibrinogen, INR, PT, and aPTT) (results to be submitted to central laboratory)
- Eye exam performed by investigator
- Blood sample for PK evaluation (168 hours \pm 24 hours after the end of infusion)
- Blood sample for plasma proteomic analysis (168 hours \pm 24 hours after the end of infusion)
- Parts A and B, US patients only: PRO-CTCAE patient-reported outcomes questionnaire

6.3.5 Cycle 1 and 2, Day 15

- Blood sample for PK evaluation (336 hours \pm 24 hours after the end of infusion)
- Blood sample for plasma proteomic analysis (336 hours \pm 24 hours after the end of infusion)
- Parts A and B, US patients only: PRO-CTCAE patient-reported outcomes questionnaire

6.3.6 Cycle 2, Day 8 (± 1 day)

- Blood sample for PK evaluation (168 hours ± 24 hours after the end of infusion)
- Blood sample for plasma proteomic analysis (168 hours ± 24 hours after the end of infusion)
- Parts A and B, US patients only: PRO-CTCAE patient-reported outcomes questionnaire

6.4 Treatment Period (Dose-Dense Regimen only)

6.4.1 Day 1 (± 1 day), All Treatment Cycles (Exceptions Noted)

- Cycle 1 only: Prior to dosing, confirm patient eligibility per inclusion/exclusion criteria
- Weight
- Physical Exam
- Predose vital signs
- ECOG Performance status (If Baseline Visit activities occur within 1 day prior, this assessment does not need to be repeated at Cycle 1, Day 1)
- Chemistry panel (results to be submitted to central laboratory; if Baseline Visit activities occur within 1 day prior, this assessment does not need to be repeated at Cycle 1, Day 1)
- CBC with differential (results to be submitted to central laboratory; if Baseline Visit activities occur within 1 day prior, this assessment does not need to be repeated at Cycle 1, Day 1)
- Pregnancy test for patients of childbearing potential (If Baseline Visit activities occur within 1 day prior, this assessment does not need to be repeated at Cycle 1, Day 1)
- Coagulation parameters (fibrinogen, INR, PT, and aPTT) (results to be submitted to central laboratory; if Baseline Visit activities occur within 1 day prior, this assessment does not need to be repeated at Cycle 1, Day 1)
- Eye exam performed by investigator
- Predose blood sample for PK evaluation (within 24 hours) (Cycles 1, 2, 3, 4, 7, and every 3rd cycle thereafter)
- Predose blood sample for ATA evaluation (within 24 hours) (Cycles 1, 2, 3, 4, 7, and every 3rd cycle thereafter)
- Predose blood sample for plasma proteomic analysis (within 24 hours) (Cycles 1, 2, 3, 4, 7, and every 3rd cycle thereafter)
- Predose blood sample for plasma mutational analysis (within 24 hours) (Cycles 1, 2, 3, 4, 7, and every 3rd cycle thereafter)
- Predose blood sample for plasma exosome analysis (within 24 hours) (Cycles 1, 2, 3, 4, 7, and every 3rd cycle thereafter)
- Predose blood sample for PBMC immune subsets analysis (within 24 hours) (Cycles 1, 2, 3, and 4 only)

- Ocular premedication and preventative eye therapy (see Section 5.4 and Appendix C)
- Ensure patient completes dosing diary
- Parts A and B, US patients only: patient-reported outcomes questionnaires (all questions). If Baseline Visit activities occur within 1 day prior, this assessment does not need to be repeated at Cycle 1, Day 1.
- Tisotumab vedotin administration
- Blood samples for PK evaluation (all time points from end of infusion)
 - End of infusion (+ 15 minutes) (Cycles 1, 2, 3, 4, 7 and every 3rd cycle thereafter)
 - 1 hour (\pm 15 minutes) (Cycle 1 only)
 - 5 hours (\pm 2 hours) (Cycle 1 only)
- Blood samples for plasma proteomic analysis (all time points from end of infusion)
 - 1 hour (\pm 15 minutes) (Cycle 1 only)
 - 5 hours (\pm 2 hours) (Cycle 1 only)

6.4.2 Cycles 1 and 2, Day 2

- Preventative eye therapy (see Section 5.4 and Appendix C)
- Ensure patient completes dosing diary

6.4.3 Cycles 1 and 2, Day 3

- Preventative eye therapy (see Section 5.4 and Appendix C)
- Blood sample for PK evaluation (48 hours \pm 4 hours after the end of infusion)
- Blood sample for plasma proteomic analysis (48 hours \pm 4 hours after the end of infusion)
- Ensure patient completes dosing diary

